#### **5.1.3.3 Prior therapies date imputation**

No imputation will be made to the start and end date of prior therapy.

#### **5.1.3.4 Post therapies date imputation**

No imputation will be made to the start and end date of post therapy.

### 5.1.3.5 Other imputations

#### Start data of medical history

Partial dates are allowed for the start date of the medical history. If the day is missing, 15th will be imputed. If the month and day are missing, July 1st will be imputed. If the year is missing, it will be treated as a missing value.

## 5.2 AEs coding/grading

AEs are coded using the MedDRA terminology.

## 5.3 Laboratory parameters derivations

NA

## 5.4 Clinically notable laboratory values and vital signs

The following defined notable laboratory or vital sign abnormalities will be used.

#### Newly occurring selected notable laboratory abnormalities :

- Albumin: < LLN
- >3x-, 5x-, 8x-, 10x-, and 20x-ULN elevations of AST, ALT, and either ALT or AST\*
- Any elevations of bilirubin > ULN; elevated bilirubin to >1.5xULN, and to >2xULN\*
- Any elevations of ALP >1.5xULN, >2xULN, >3xULN, >5xULN \*
- Elevation of AST and/or ALT (>3xULN, >5x-, >10x) accompanied by elevated bilirubin (>2xULN)\*
- ALT or AST >3x ULN and TBL >2x-, and ALP <2xULN
- ALP >3x-, 5x ULN and TBL >2xULN
- Gamma-Glutamyl transferase (GGT): > ULN, 3 x ULN, 5 x ULN
- Creatinine (serum):  $\geq 1.5 \times \text{ULN}$
- Creatinine clearance (Cockcroft-Gault formula‡):
  - $\geq 25\%$  decrease from baseline†
  - $\geq 25\%$  decrease from baseline† and  $\geq 3$  months in duration§
  - $\geq 25\%$  decrease from baseline† in combination with protein urine dipstick resulting in new protein  $\geq 1+$  and  $\geq 3$  months in duration§
- Potassium:  $\geq 5.5 \text{ mmol/L}$ , or  $\leq 3.0 \text{ mmol/L}$
- Magnesium:  $\geq 1.5 \text{ mmol/L}$ , or  $\leq 0.5 \text{ mmol/L}$
- Sodium:  $\geq 150 \text{ mmol/L}$ , or  $\leq 130 \text{ mmol/L}$
- Calcium:  $\geq 1.2 \times \text{ULN}$  or < LLN

- Hemoglobin:  $\geq 2$  g/dL decrease from baseline, or  $< 10.0$  g/dL
- Criteria based on CTC grades for hemoglobin: Grade 1 ( $< \text{LLN} - 100$  g/L), Grade 2 ( $< 100 - 80$  g/L), Grade 3 ( $< 80 - 65$  g/L), Grade 4 ( $< 65$  g/L)
- Platelet count:  $< \text{LLN}$
- Criteria based on CTC grades for platelet: Grade 1 ( $< \text{LLN} - 75.0 \times 10^9/\text{L}$ ), Grade 2 ( $< 75.0 - 50.0 \times 10^9/\text{L}$ ), Grade 3 ( $< 50.0 - 25.0 \times 10^9/\text{L}$ ), Grade 4 ( $< 25.0 \times 10^9/\text{L}$ )
- White blood cell count:  $\leq 0.8 \times \text{LLN}$  or  $\geq 1.2 \times \text{ULN}$
- Criteria based on CTC grades for white blood cell count: Grade 1 ( $< \text{LLN} - 3.0 \times 10^9/\text{L}$ ), Grade 2 ( $< 3.0 - 2.0 \times 10^9/\text{L}$ ), Grade 3 ( $< 2.0 - 1.0 \times 10^9/\text{L}$ ), Grade 4 ( $< 1.0 \times 10^9/\text{L}$ )
- Absolute Neutrophils:  $\leq 0.9 \times \text{LLN}$  or  $\geq 1.2 \times \text{ULN}$
- Criteria based on CTC grades for absolute neutrophils: Grade 1 ( $< \text{LLN} - 1.5 \times 10^9/\text{L}$ ), Grade 2 ( $< 1.5 - 1.0 \times 10^9/\text{L}$ ), Grade 3 ( $< 1.0 - 0.5 \times 10^9/\text{L}$ ), Grade 4 ( $< 0.5 \times 10^9/\text{L}$ )
- Absolute Eosinophils:  $\geq 1.1 \times \text{ULN}$ ,  $\geq 0.45 \times 10^9/\text{L}$
- Absolute Lymphocytes:  $< \text{LLN}$  or  $\geq 1.1 \times \text{ULN}$
- Protein urine dipstick:  $\geq ++$ , New protein  $\geq 1+$ ,  $\geq 3$  months in duration
- Total Cholesterol:  $\geq 1.5 \times \text{ULN}$
- Triglycerides:  $\geq 5.7$  mmol/L

† Baseline is defined as the mean in two consecutive visits that are  $\geq 14$  days apart. If there are not two consecutive visits that are  $\geq 14$  days apart, baseline values will be used.

§ The notable laboratory abnormalities will be assessed for each assessment and presented in the table. The duration will be picked up manually.

‡ Cockcroft-Gault formula is defined by sex as follows:

Cockcroft-Gault formula (Men):  $\text{CrCl (mL/min)} = [((140 - \text{age (years)}) \times \text{weight (kg)}) / (\text{serum creatinine}(\mu\text{mol/L}) / 88.4) (\text{mg/dL}) \times 72]$  ,

Cockcroft-Gault formula (Women):  $\text{CrCl (mL/min)} = [((140 - \text{age (years)}) \times \text{weight (kg)}) / (\text{serum creatinine}(\mu\text{mol/L}) / 88.4) (\text{mg/dL}) \times 72] \times 0.85$ .

### **Newly occurring selected notable vital signs abnormalities :**

- Systolic blood pressure:  $\geq 25\%$  decrease or  $\geq 25\%$  increase from baseline.
- Diastolic blood pressure:  $\geq 25\%$  decrease or  $\geq 25\%$  increase from baseline.
- Systolic blood pressure and Diastolic blood pressure: increase to  $\geq 140$  and  $90$ , respectively.
- Pulse:  $\geq 110$  bpm with  $\geq 15\%$  change from baseline, or  $< 50$  bpm with  $\geq 15\%$  change from baseline

\* FDA Guidance for Industry Drug-Induced Liver Injury: Premarketing Clinical Evaluation

Note: Only post-baseline values will be flagged as notable abnormalities

## 5.5 Statistical models

### Primary analysis

No statistical model will be used for the primary analysis.

### Key secondary analysis

No statistical model will be used for the key secondary analysis.

### Rule of exclusion criteria of analysis sets

The protocol deviations that cause participants to be excluded from the analyses are listed in [Table 5-1](#).

Table 5-1 Protocol deviations that cause participants to be excluded		
Deviation ID	Description of Deviation	Exclusion in Analyses
INCL01	No signed informed consent was obtained before any assessments were performed	Excluded from both FAS and Safety set
TRT02	Participant was not exposed to study medication at any visit	Excluded from both FAS and Safety set

## 5.6 Documentation of statistical methods

### 5.6.1 Calculation of prednisone equivalent dose (mg/kg/day) of oral steroids

The oral steroid dose at baseline will be the measurement on the date of baseline (Day 1) recorded on the concomitant medication page in eCRF. The oral steroid used for AOSD indication will be used. The oral steroid dose will be converted to prednisone equivalent dose using the conversion factor in [Table 5-2](#). The prednisolone equivalent dose will be derived by dividing the dose of the oral steroid dose by the corresponding conversion factor. Body weight will be the measurement at baseline (Day 1) or the last available weight before baseline.

The oral steroid dose at post-baseline assessment visits after Week 8 will be the measurement on one day before the date of corresponding assessment visits. Body weight will be the last available measurement on or before the date of steroid dose measurement.

The daily dose will be calculated by multiplying the conversion factors corresponding to the frequency recorded in eCRF (see [Table 5-3](#)). If participants use more than 2 oral steroids for AOSD on the same day, total dose per day will be used.

When a participant continued the study, if there is no concomitant oral steroid data at the assessment day, it will be considered as steroid free (0 mg).

If the oral steroid data is available but with missing information (e.g., body weight, frequency), the prednisone equivalent dose will be set to missing.

For example, if a participant weighs  $w$  kg and is taking  $x$  mg of Betamethasone 2 times per day and  $y$  mg of Hydrocortisone 3 times per day, the prednisone equivalent dose will be calculated as follows:

Prednisone equivalent dose per day =  $(x/0.12*2 + y/4*3)/w$ .

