6. With underlying metabolic, renal, hepatic, infectious or gastrointestinal conditions which in the opinion of the investigator compromises the participant and/ or places the participant at unacceptable risk for participation in an immunomodulatory therapy.
7. Clinical evidence of liver disease or liver injury as indicated by abnormal liver function tests at screening such as Aspartate Aminotransferase (AST), Alanine Aminotransferase (ALT), Gamma-glutamyl transferase (GGT), alkaline phosphatase (ALP)(must not exceed 3 times the upper limit value of the normal range for age), or serum bilirubin (must not exceed twice the upper limit value of the normal range for age). Exception: participants who exceed this limit after initiating latent TB treatment may be eligible for participation in this study pending confirmation with Novartis.
8. Presence of moderate to severe impaired renal function as indicated by clinically significantly abnormal creatinine ($\geq 1.5 \times$ upper normal limit ULN) or abnormal urinary constituents (e.g., albuminuria) at screening. Evidence of urinary obstruction or difficulty in voiding at screening.
9. Use of concomitant treatments including disease-modifying and/or immunosuppressive drugs with the exception of:
 - Stable daily dose of systemic corticosteroid treatment ≥ 10 mg AND ≤ 1.0 mg/kg/day (maximum 60 mg/day) of oral prednisone (or equivalent) for at least 1 week prior to baseline
 - Stable dose of no more than one non-steroidal anti-inflammatory drug (NSAID) for at least 1 week prior to the baseline visit
 - Stable dose of methotrexate (maximum of 20 mg/m²/week) for at least 4 weeks prior to the baseline visit, and folic/folinic acid supplementation (according to standard medical practice of the center)
10. Use of following therapies:
 - Anakinra within 24 hours prior to baseline visit
 - Rilonacept within 1 week prior to baseline visit
 - Tocilizumab within 3 weeks prior baseline
 - Etanercept within 4 weeks prior baseline
 - Infliximab within 12 weeks prior to the baseline visit
 - Golimumab within 12 weeks prior to the baseline visit
 - Adalimumab within 8 weeks prior to the baseline visit
 - Abatacept within 10 weeks prior to the baseline visit
 - Rituximab within 26 weeks prior to the baseline visit

- Leflunomide within 4 weeks prior to the baseline visit. Documentation of a completion of a full cholestyramine elimination treatment after most recent leflunomide use will be required.

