8.3.2 Corticosteroid tapering

Participants using concomitant corticosteroids at study entry may begin to reduce their corticosteroid dose to the lowest possible dose/discontinuation beginning at Week 8 until the End of Study as detailed in [Section 6.2.1.1](#) of the protocol.

Successful oral corticosteroid tapering is defined as meeting one of the following:

- Participants with prednisone equivalent dose of > 0.8 mg/kg/day at baseline were able to reduce their dose to ≤ 0.5 mg/kg/day.
- Participants with prednisone equivalent dose from ≥ 0.5 mg/kg/day and ≤ 0.8 mg/kg/day at baseline were able to reduce their dose by at least 0.3 mg/kg/day.
- Participants with any initial prednisone equivalent dose at baseline were able to reduce their dose to ≤ 0.2 mg/kg/day.
- Participants with prednisone equivalent dose of ≤ 0.2 mg/kg/day at baseline were able to reduce their dose with any reduction

AND maintaining a minimum adapted ACR30 response.

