12.5 Analysis supporting secondary objectives

12.5.1 Key efficacy endpoint

The secondary estimand is the effect of canakinumab on oral corticosteroids tapering starting from Week 8 to Week 28. Successful tapering of corticosteroids will be derived on prednisone equivalent dose per day (mg/kg/day) as described in [Section 8.3.2](#). Further details will be described in the statistical analysis plan.

Frequency table with the number and percentage of participants who were able to taper oral corticosteroids successfully at Week 28 will be provided for the FAS. The participants who used systemic corticosteroid at baseline and were administered study treatment at Week 8 will be considered in this analysis.

The analysis will account for different intercurrent events as explained in the following:

1. Discontinuation of study treatment after Week 8 for any reason: If a participant early discontinued study treatment after Week 8 but had the Week 28 assessment regarding corticosteroid tapering, he/she will be included in the analysis.
2. Intravenous administration of steroid at any time between Week 8 and Week 28: If a participant had intravenous administration of steroid at any time between Week 8 and Week 28, he/she will be considered as corticosteroid tapering failure (non-responder imputation)

If the successful tapering of corticosteroids cannot be derived due to missing body weight, it will be imputed with the last available data from Week 8 to Week 28 (last observation carried forward (LOCF) approach).

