

• To evaluate the pharmacokinetics (PK) / pharmacodynamic (PD) of canakinumab

	

• Means and mean change over time of:

-Vital sign parameters

-Laboratory parameters

• Canakinumab concentrations over time

• Total IL-1<math>\beta</math> (sum of IL-1<math>\beta</math> free and bound to canakinumab) level s over time

• To assess the immunogenicity of canakinumab

	

• Anti-canakinumab antibody identification and titer at BSL, Week 24, Week 48 and every 24 weeks until EOS.

Exploratory objective(s)	Endpoint(s) for exploratory objective(s)

Successful oral corticosteroids tapering is defined as meeting one of the following in terms of prednisone equivalent dose per day (mg/kg/day).

- Participants with prednisone equivalent dose of  $> 0.8$  mg/kg/day at baseline were able to reduce their dose to  $\leq 0.5$  mg/kg/day.
- Participants with prednisone equivalent dose from  $\geq 0.5$  mg/kg/day and  $\leq 0.8$  mg/kg/day at baseline were able to reduce their dose by at least 0.3 mg/kg/day.
- Participants with any initial prednisone equivalent dose at baseline were able to reduce their dose to  $\leq 0.2$  mg/kg/day.
- Participants with prednisone equivalent dose of  $\leq 0.2$  mg/kg/day at baseline were able to reduce their dose with any reduction.

AND maintaining a minimum adapted ACR30 response.

Details on how to calculate the prednisone equivalent dose per day are given in [Section 5.6.1](#).

Unless otherwise stated, the terms “prednisone equivalent dose” means prednisone equivalent dose of oral steroids.

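### Tapering success is judged in mg/kg/day with different body weights at baseline and follow-up, so near a cut-off a weight change alone can decide the result

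*SAP*

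**What the plan says.** Protocol 12.5.1 and SAP 1.2 both derive tapering success on the prednisone-equivalent dose in mg/kg/day. Protocol 8.3.2 and SAP 1.2 list the same four dose criteria, of which one must be met:

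1. baseline above 0.8: down to 0.5 or less;
2. baseline 0.5 to 0.8: a fall of at least 0.3;
3. any baseline dose: down to 0.2 or less;
4. baseline 0.2 or less: success if participants "were able to reduce their dose with any reduction".

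An adapted ACR30 response must also be maintained. Under SAP 2.6.1, i.v. steroid between Week 8 and Week 28 counts as failure.

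SAP 5.6.1 sets the denominators. At baseline, "Body weight will be the measurement at baseline (Day 1) or the last available weight before baseline". For visits after Week 8, the dose "will be the measurement on one day before the date of corresponding assessment visits", and "Body weight will be the last available measurement on or before the date of steroid dose measurement". No section fixes the weight for this endpoint or requires the mg/day dose to be lower than at baseline.

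**The concern.** The endpoint is meant to show that participants need less steroid. When the two doses are divided by different weights, the computed change mixes the change in tablets taken with the change in body weight. This matters most under criterion 4, which sets no minimum reduction, and for anyone whose dose lands on a cut-off.

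The tapering guideline in Protocol Table 6-2 works in steps of 0.1 mg/kg, so doses can fall exactly on the cut-offs. Three steps down from 0.8 give 0.5, which is a fall of exactly 0.3.

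At stake is the key secondary rate of a small single-arm study that supports a registration dossier. No comparator arm would share the error.

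**Working it through.** The documents give no expected tapering rate and no weight-change data, so there is no figure of the plan's own to reproduce. The check applies the four criteria directly.

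**Unchanged mg/day dose.** Let d0 be the baseline dose in mg/kg/day, and W0 and W28 the two weights. If the mg/day dose does not change, the Week 28 dose is d0 × W0/W28. The weight gain that is enough to meet a criterion is:

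- criterion 4 (d0 ≤ 0.2): any gain above zero;
- criterion 3 (d0 > 0.2): d0/0.2 − 1;
- criterion 2 (d0 from 0.5 to 0.8): d0/(d0 − 0.3) − 1;
- criterion 1 (d0 > 0.8): d0/0.5 − 1.

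| Baseline dose (mg/kg/day) | Smallest weight gain that gives success |
|---|---|
| ≤ 0.20 | any |
| 0.205 | 2.5% |
| 0.21 | 5% |
| 0.22 | 10% |
| 0.25 | 25% |
| 0.30 | 50% |
| 0.50 | 150% |
| 0.80 | 60% |
| 1.00 | 100% |

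From 0.5 upward the smallest value is 60%, at 0.80. For an assumed gain g, the highest affected baseline dose is 0.2 × (1 + g): 0.21 at 5%, 0.22 at 10%, 0.24 at 20%.

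**Examples with no steroid removed:**

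- 10 mg/day, 60.0 to 60.1 kg: 0.1667 to 0.1664. Meets criterion 4.
- 10 mg/day, 49 to 50 kg: 0.2041 to 0.2000. Meets criterion 3.
- 12.5 mg/day, 60 to 63 kg: 0.2083 to 0.1984. Meets criterion 3.
- 15 mg/day, 60 to 66 kg: 0.2500 to 0.2273. Meets none.

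**Who can be in the lowest band.** Protocol 5.2 item 9 allows a "Stable daily dose of systemic corticosteroid treatment" of at least 10 mg. Since 10/0.2 = 50, a baseline of 0.2 or less needs a weight of at least 50 kg. At 60 kg it means 10 to 12 mg/day (0.2 × 60 = 12).

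**Partial tapers at a cut-off:**

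- 48 to 30 mg/day at a constant 60 kg: 0.80 − 0.50 = 0.30, success. With weight down to 57 kg: 0.80 − 0.526 = 0.274, failure.
- 40 to 22.5 mg/day at a constant 60 kg: 0.667 − 0.375 = 0.292, failure. With weight up to 61.5 kg: 0.667 − 0.366 = 0.301, success.
- 24 to 12 mg/day at a constant 60 kg: reaches 0.200, success. With weight down to 59.5 kg: 0.2017, failure.
- 54 to 30 mg/day at a constant 60 kg: 0.90 to 0.500, success. With weight down to 57 kg: 0.526, failure.

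**A related ambiguity.** These results read criterion 3 as needing an actual reduction. If it is programmed only as a Week 28 dose of 0.2 or less, an unchanged dose at unchanged weight passes for anyone already at or below 0.2, and criterion 4 becomes redundant. Fixing the weight alone would not cure that.

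**Size per participant.** 1/11 = 9.1 points for the first-11 analysis and 1/14 = 7.1 points for all 14. It is larger if fewer are evaluable, which SAP 2.6.2 allows for.

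**The case against.** **The effect is confined to an edge.** This stands. A reader might infer that anyone who gains weight on an unchanged dose is classed as tapered. The table shows otherwise: above about 0.22 to 0.25 mg/kg/day the gain needed is 10% to 25% or more, and from 0.5 upward at least 60%. Weight gain is also never sufficient alone, because adapted ACR30 must be maintained and i.v. steroid is failure. These conditions narrow the group at risk, but neither tests whether the dose fell.

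**The tapering guidance makes the case unusual.** Partly stands. Under Protocol 6.2.1.1 a participant at 0.167 mg/kg/day could be off steroid in about 4 weeks, and 20 weeks are available between Week 8 and Week 28. A responder still on exactly the baseline dose is therefore not the expected course. It remains possible, because tapering depends on the investigator's judgement. The partial-taper cases do not need an unchanged dose at all.

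**Weight-free results are already planned.** True: SAP 2.7.2 summarises dose change in mg/day, SAP 2.14 adds tapering below 5 mg/day, and SAP 2.6.2 separates tapered from steroid-free. SAP 2.3.2 tabulates baseline dose with a category for 0.2 or less, so the exposed group will be visible. None of this corrects the key secondary rate itself.

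**Current weight agrees with the protocol.** Protocol 12.5.1 carries forward weights from Week 8 to Week 28, so it does expect post-baseline weights. The plan is not contradicting itself, and fixing the weight would be a change to the specified derivation. This stands and shapes the fix.

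**A late redefinition could be informed by the data.** This also stands. The study is open-label, SAP 2.14 dates the first-11 data point to 6 December 2022, and SAP 2.8.1.1 cites a source of 2 October 2023.

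**Conclusion.** The rule in SAP 5.6.1 can give a wrong classification, in a limited region: unchanged doses at or just above 0.2 mg/kg/day, and partial tapers that land on the 0.2, 0.3 or 0.5 cut-offs. The upper limit for unchanged doses rests on an assumed weight gain (0.21 at 5%, 0.22 at 10%, 0.24 at 20%).

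Each misclassified participant costs 9.1 or 7.1 points. That is a per-participant figure, not an expected bias: the documents do not give the number of participants at or below 0.2 mg/kg/day. The weighing rows of the assessment schedule are not in the text available for this review, so how recent the follow-up weight would be could not be checked.

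Two stronger readings are not supported. A reader might infer that the error mostly favours the drug, since weight gain on steroids seems plausible. The documents contain no weight-change data, and the examples run both ways, so the net direction is unknown. A reader might also infer a threat to the trial's main conclusion. The tapering endpoint is a descriptive frequency table with no test, and the only planned hypothesis test, adapted ACR30 at Week 8, does not use this derivation. The severity is moderate.

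**What to change.** In SAP 5.6.1, for the success criteria only:

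- divide both the baseline and the post-baseline dose by the baseline (Day 1) weight;
- count success only if the prednisone-equivalent mg/day dose is below its baseline value. At an unchanged dose the computed change is then zero whatever the weight does. This also settles criterion 3 for participants already at or below 0.2 mg/kg/day.

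Record both in SAP section 4, which now lists no changes, as a departure from the derivation in Protocol 8.3.2 and 12.5.1. Because open-label data have already accrued, report the derivation as now written alongside, so that a reader can see how many participants differ.

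The cost is one extra tabulation and no new data, since the mg/day dose is already derived. The success rate may come out slightly lower. Carrying forward post-baseline weights is no longer needed, but SAP 2.6.3 would still carry forward for other missing information, such as dosing frequency.

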**Table 5-2 Conversion factors for steroid medications**

Medication	Conversion factor
Betamethasone	0.12
Hydrocortisone	4
Cortisone	5
Deflazacort	1.2
Dexamethasone	0.15
Methylprednisolone	0.8
Prednisolone	1
Triamcinolone	0.8
Prednisone	1

**Table 5-3 Conversion factors for frequencies**

Frequency	Conversion factor
2 Times per day	2
Every month	1/28
As needed	1
Every 24 hours	1
Every other day	1/2
3 Times per day	3
4 Times per day	4
Once	1
Daily	1
Every week	1/7
2 Times per week	2/7
3 Times per week	3/7
4 Times per week	4/7
Per annum	1/365.25
Every 4 hours	6
Every 6 hours	4
Every 8 hours	3
Unknown	Missing
Other	Missing

### 5.6.2 DAS28-CRP

The Disease Activity Score (DAS28) ([Prevoo et al 1995](#); [Fransen et al 2003](#)) is a combined index to measure the disease activity in patients with Rheumatoid arthritis.

#### Calculation of DAS28-CRP

The following formula to calculate the DAS28 using standardized CRP (mg/L) will be used:

$$\text{DAS28-CRP} = 0.56 * \sqrt{28 \text{ Tender joint count}} + 0.28 * \sqrt{28 \text{ Swollen joint count}} + 0.36 * \ln(\text{standardized CRP in mg/L} + 1) + 0.014 * \text{Participant's assessment of disease activity (Participant's overall well-being) (0-100mm)} + 0.96$$

The score will be calculated only when all components are available. If any component measurement is missing, DAS28-CRP will be missing. The following 28 joints will be assessed for tenderness and swelling: metacarpophalangeal I-V(10), thumb interphalangeal (2), hand proximal interphalangeal II-V (8), wrist (2), elbow(2), shoulders (2), and knees (2).

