8.3.1.5 C-reactive protein (CRP)

C-reactive protein will be determined in order to identify the presence of inflammation, to determine its severity, and to monitor response to treatment. Analytes will be measured at the local lab. The actual sample collection date and time and result will be entered on the tablet device.

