8.3.5 DAS28-CRP

The DAS28-CRP is a measure of disease activity in Rheumatoid arthritis (RA) based on Swollen and Tender Joints Counts (out of a total of 28), CRP and the Patient's Global

Assessment of Disease ([Prevoo et al 1995](#); [Fransen et al 2003](#)). DAS28-CRP is a composite index, validated for RA patients and takes into account the following items: Tender joint count (number of tender joints; 0-28); swollen joint count (number of swollen joints; 0-28); C-reactive protein (mg/l) and Global Health (Patient's Global Assessment of Disease Activity; from 0=best to 100=worst). Thus, given the reliability, validity, and ability of DAS28 to discriminate the severity of joint involvement, this index has been used in other rheumatic diseases characterized by RA-like poly-articular involvement. Of note, a DAS28 score > 5.1 implies active disease, ≤ 3.2 low disease activity, and < 2.6 remission. Moderate/high disease activity is defined as a DAS28 higher than 3.2.

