#### **Continuous variables:**

- Body temperature (°C)
- Time from AOSD diagnosis to study entry (screening visit) (years)
- Standardized C-reactive protein (CRP)\*1 (mg/L)
- Oral prednisone equivalent dose at baseline (mg/day)
- Oral prednisone equivalent dose at baseline (mg/kg/day)
- Physician's global assessment of disease activity (VAS) (mm)
- Participant's assessment of disease activity (Participant's overall well-being) (VAS) (mm)
- Participant's assessment of disease activity (Pain) (VAS) (mm)
- Number of active joints (68 joints evaluated for pain/tenderness and 66 for swelling)\*2

- Number of tender joints
- Number of swollen joints
- HAQ functional ability score
- DAS28-CRP
- CCI
- Systemic feature score
- Ferritin (ug/L)

\*1 Standardized C-reactive protein (CRP) (mg/L) will be calculated based on the SI normal range of 0.0-10.0 mg/L using the following formula:

Standardized CRP =  $10 \times [(\text{observed CRP value} - \text{minOMU}) / \text{rangeOMU}]$ ,

where minOMU and rangeOMU are minimum value and range of normal range on the original measurement unit respectively.

\*2 The number of active joints is defined as the number of joints that are tender or swollen.

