#### Categorization of DAS28-CRP

High disease activity:	DAS28 at the timepoint > 5.1
Moderate disease activity:	$3.2 \leq \text{DAS28 at the timepoint} \leq 5.1$
Low disease activity:	$2.6 \leq \text{DAS28 at the timepoint} < 3.2$
Remission:	DAS28 at the timepoint < 2.6

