#### EULAR response criteria (based on DAS28-CRP)

Good response:	$\Delta \text{DAS28} > 1.2$ and DAS28 at the timepoint $\leq 3.2$
Moderate response:	$\Delta \text{DAS28} > 1.2$ and DAS28 at the timepoint $> 3.2$ or $0.6 < \Delta \text{DAS28} \leq 1.2$ and DAS28 at the timepoint $\leq 5.1$
No response:	$\Delta \text{DAS28} \leq 0.6$ or $0.6 < \Delta \text{DAS28} \leq 1.2$ and DAS28 at the timepoint $> 5.1$

where  $\Delta \text{DAS28}$  is the improvement in DAS28 from baseline.

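### SAP 5.6.2 puts CRP rescaled to each local laboratory's normal range into the DAS28-CRP formula, so scores and categories shift wherever that range is not exactly 0-10 mg/L

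*SAP*

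**What the plan says.** Protocol 8.3.5 lists the components of DAS28-CRP and includes "C-reactive protein (mg/l) and Global Health". It mentions no rescaling and prints no formula. It attaches interpretive thresholds to the score: above 5.1 for active disease, then 3.2, and finally "low disease activity, and < 2.6 remission". On where CRP comes from, protocol 8.3.1.5 says: "Analytes will be measured at the local lab".

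SAP 5.6.2 supplies the formula and introduces it with "The following formula to calculate the DAS28 using standardized CRP (mg/L) will be used". Footnote 1 of SAP 2.3.2 says that standardized CRP "will be calculated based on the SI normal range of 0.0-10.0 mg/L using the following formula". The formula is 10 x (observed - minOMU)/rangeOMU, "where minOMU and rangeOMU are minimum value and range of normal range on the original measurement unit respectively".

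The SAP then applies fixed cut-offs to the result. Remission is "DAS28 at the timepoint < 2.6", and 3.2 and 5.1 separate the other activity categories. EULAR response combines those levels with thresholds of 0.6 and 1.2 on a quantity that "is the improvement in DAS28 from baseline".

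Elsewhere the SAP treats observed CRP as a separate quantity: in SAP 2.7.2 the baseline CRP criterion of the systemic feature score is marked as observed. SAP Section 4, on changes to the protocol-specified analyses, reads NA.

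**The concern.** Standardized CRP measures position relative to a laboratory's normal range. It is not a concentration, although SAP 5.6.2 labels it mg/L. The formula is non-linear in CRP and is read against fixed cut-offs, so a multiplicative rescaling of CRP changes the score itself and not merely its units.

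Change in DAS28-CRP is a secondary endpoint (protocol Table 2-1). DAS28-CRP, DAS28-CRP response and EULAR response by visit are all in the SAP 2.14 list for the analysis of the first 11 participants. DAS28-CRP by visit is also split by prior tocilizumab use in those 11 (SAP 2.2.1). With 11 participants, one reclassification moves a proportion by 1/11 = 9.1 percentage points; with the 14 in SAP 2.5.6, by 1/14 = 7.1 points. Scores on rescaled CRP would also not be comparable with DAS28-CRP calculated on mg/L.

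**Working it through.** The documents state no DAS28-CRP figure to reproduce, so the check applies the SAP's own two formulas.

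**Inputs**
- Rescaling (SAP 2.3.2): standardized CRP = 10 x (c - L)/(U - L), where c is observed CRP in mg/L and L and U are the laboratory's normal limits.
- Score (SAP 5.6.2): 0.56 x sqrt(tender) + 0.28 x sqrt(swollen) + 0.36 x ln(CRP + 1) + 0.014 x well-being + 0.96.
- Local limits: not in the documents. Assumed L = 0, with U varied from 1.5 to 15 mg/L.

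**Shift in level.** With L = 0, only the CRP term differs:

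shift = 0.36 x [ln(10c/U + 1) - ln(c + 1)]

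For U = 3:
- c = 1: 0.36 x [ln 4.333 - ln 2] = 0.278
- c = 50: 0.36 x [ln 167.67 - ln 51] = 0.428

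**Shift in improvement.** This is the shift at baseline minus the shift at the visit. For U = 3 and a fall from 50 to 1, it is 0.428 - 0.278 = 0.150.

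| U (mg/L) | Level, CRP 0.5 | CRP 1 | CRP 5 | CRP 50 | CRP 100 | Improvement, 50 to 1 | 50 to 5 |
|---|---|---|---|---|---|---|---|
| 1.5 | +0.38 | +0.48 | +0.63 | +0.68 | +0.68 | +0.19 | +0.05 |
| 3 | +0.21 | +0.28 | +0.39 | +0.43 | +0.43 | +0.15 | +0.04 |
| 5 | +0.10 | +0.15 | +0.22 | +0.25 | +0.25 | +0.10 | +0.03 |
| 8 | +0.03 | +0.04 | +0.07 | +0.08 | +0.08 | +0.04 | +0.01 |
| 10 | 0 | 0 | 0 | 0 | 0 | 0 | 0 |
| 15 | -0.04 | -0.07 | -0.12 | -0.14 | -0.14 | -0.08 | -0.03 |

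**Can a category change?** Two constructed participants show that it can.

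1. Remission. A visit with 1 tender joint, 1 swollen joint, CRP 3 mg/L and well-being 15 mm.
   - Observed CRP: 0.56 + 0.28 + 0.36 x ln 4 + 0.21 + 0.96 = 2.51, remission.
   - U = 3: standardized CRP is 10 and the score is 2.87, low disease activity.
   - U = 5: 2.71. U = 10: 2.51. U = 15: 2.41.
   - The same patient is therefore in remission at a site with U = 10 and not in remission at a site with U = 3.
2. EULAR response. Baseline has 2 tender and 2 swollen joints, CRP 30 and 30 mm; the visit has 2 and 2, CRP 1 and 25 mm.
   - Observed CRP: 3.804 - 2.747 = 1.057, moderate response.
   - U = 3: 4.229 - 3.026 = 1.204 (unrounded scores). This exceeds 1.2 with a visit score below 3.2, so it is a good response.

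**Two side effects**
- If L is above 0, standardized CRP can be negative. A range of 0.5-3.0 with an observed 0.2 gives 10 x (0.2 - 0.5)/2.5 = -1.2, and the logarithm is undefined.
- A participant whose local laboratory changes during the study acquires a spurious change in score.

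**Effect on percent change in CRP.** With L = 0 and one laboratory throughout, the factor 10/U cancels: 50 to 5 is -90% on either scale. The CRP component of adapted ACR is then unaffected.

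**The case against.** The strongest defence has four parts.

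- **The protocol left the formula open.** Protocol 8.3.5 prints none, and protocol Section 12 leaves further statistical detail to the SAP. Whether the coefficients and cut-offs were calibrated on raw mg/L depends on publications not available here. This stands in part: the SAP was entitled to supply the formula. But the protocol names mg/L as the unit and gives the cut-offs for that score, so a different CRP quantity should at least be declared in SAP Section 4.
- **Standardizing across local laboratories is a recognizable aim.** That is so for summaries of CRP itself. It does not justify rescaling values already in mg/L inside a formula with fixed coefficients and cut-offs. The systemic feature score compares observed CRP with a fixed 10 mg/L threshold. That use is natural for an absolute threshold and is no error in itself, but it shows that the SAP accepts observed values across laboratories.
- **The size is assumed.** This stands. No passage gives a reference range or shows that ranges differ between sites. If every site used 0-10 mg/L, the effect would be nil.
- **The consequence is limited.** This also stands. The protocol endpoint is change from baseline, where the shifts partly cancel. The activity categories and EULAR response are SAP additions, none of these outputs is tested, and only participants near a threshold can move.

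A reader might infer that rescaling raises every score and always flatters the drug. The documents do not support that. Both statements need an upper limit below 10 mg/L, and both reverse above it. Even below 10 the effects oppose each other: higher levels make remission harder to reach, while improvement is inflated.

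**Conclusion.** The inconsistency is in the text. SAP 5.6.2 uses a quantity that is CRP in mg/L only for a 0-10 mg/L local range, labels it mg/L, and reads the result against fixed cut-offs.

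The size and direction are conditional on local ranges that the documents do not give. Assuming a lower limit of 0, the level shifts by up to about +0.4 at an upper limit of 3 and about +0.25 at 5, by nothing at 10, and by -0.04 to -0.14 at 15 (CRP 0.5 to 100 mg/L). Improvement shifts less: at an upper limit of 3, by +0.15 when CRP falls from 50 to 1 and by +0.04 when it falls from 50 to 5.

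A reader might go on to doubt the primary result. This point gives no ground for that when the lower limit is 0 and the participant's laboratory stays the same. It should be corrected because the small sample makes single reclassifications visible and the remedy is cheap, but it concerns secondary, descriptive outputs only.

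**What to change.** In SAP 5.6.2, define the CRP term as observed CRP converted to mg/L, and derive the activity categories and EULAR response from that score. Keep standardized CRP for the baseline and adapted ACR component summaries and for the output on CRP within the normal range. If the sponsor prefers standardization in DAS28-CRP, record it with a reason in SAP Section 4 and present both versions.

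The cost is one definition, one program variable and a rerun of the DAS28 outputs. No new data are needed, because observed CRP is already used for the systemic feature score. The small downside is that DAS28-CRP and the adapted ACR component summaries will rest on different versions of CRP; the SAP already carries two versions.
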